## 9.6 Analyses

### 9.6.1 General Analysis Considerations

The following sections provide a brief overview of the analysis considerations for REPRIEVE (A5332). Prior to the start of enrollment, a detailed Statistical Analysis Plan fully delineates all planned statistical analyses. **In the event of a DSMB recommendation to stop the trial for efficacy at interim review, full analysis and publication of the primary trial results will be prepared based on the frozen data for the DSMB meeting. Subsequent analyses (including a database prepared for future data-sharing requests) will be performed based on the final trial database including all final study termination visits. In the event of a DSMB recommendation to stop for futility, full analysis and publication of the primary trial results will be performed based on the final trial database including all final study termination visits.**

All major treatment comparisons between the randomized groups will be performed according to the principle of "intention-to-treat;" that is, participants will be analyzed (and endpoints attributed) according to the randomized treatment assigned regardless of subsequent changes to that treatment; as-treated analyses will also be performed. Descriptive summaries of the distribution of continuous baseline variables will be presented in terms of percentiles (eg, median, 25th and 75th percentiles), while discrete variables will be summarized in terms of frequencies and percentages. Statistical comparisons will be performed using two-sided significance tests with a 5% Type I error.

Unless otherwise noted, comparison of time to event outcomes will use methods for competing risks, notably Cox proportional hazards models for estimation of cause-specific hazard ratios and Gray's test for comparison of cumulative incidence curves.

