## 9.5 Analysis Plan

### 9.5.1 General analysis considerations

The presence and extent of coronary artery disease (CAD) in this population will be described including non-obstructive or obstructive CAD, volume of NCP and calcified plaque, and Agatston score, as well as the prevalence of high risk plaque features such as positive remodeling and low CT attenuation, and levels of inflammatory, and immunomodulatory biomarkers. 95% confidence intervals will be provided for CAD characteristic for the mechanistic study subgroup as whole and by randomization.

All treatment group comparisons will be performed ITT using a 5% type error. Unless otherwise noted, analyses will be performed by subgroups defined according to the presence of NCP at study entry. Since CCTA will not be available at the time of randomization, balance by treatment arm cannot be guaranteed within these subgroups, but given the large sample size and stratification according to sex and HIV-1 disease severity relative balance between the group sample sizes is expected.

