##### 3.2.2 Progression of NCP over 2 years (Primary)

- Binary outcome (Yes, No)
- Based on both quantitative and qualitative reads
  - Among participants without evidence of NCP at entry on the qualitative read, evidence of NCP at 2 years.
  - Among participants with evidence of NCP at entry on qualitative read, >0% increase in NCP volume
  - Participants with discordant outcomes based on qualitative and quantitative reads, progression will be defined by the quantitative read.

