## 7 Analysis Plan

### 7.1 General analysis Considerations

Outcome distributions will be described with median, Q1, Q3, P10, P90, minimum, and maximum and shown graphically. All primary treatment group comparisons will be performed ITT using a 5% type error. For continuous outcomes, inference will be based on differences in means adjusted for baseline and presented with two-sided, 95% confidence intervals.

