#### Table: Primary and secondary plaque outcomes

Among participants with plaque at entry, descriptive statistics for the change and percentage change in NCP volume over 2 years will be provided by treatment group with group comparisons made with linear regression with adjustment for baseline plaque volume and stratified by sex and CD4.

Among those without NCP at entry, the prevalence of incident NCP over 2 years will be compared with stratified chi-squared test.

To assess the mechanistic study population as a whole, the probability of NCP and total plaque progression over two years (see Section 3.2.2) will be compared by treatment group using a stratified chi-squared test.

The statin effect on high risk plaque features (any), including low attenuation and positive remodeling, will be assessed by comparing differences in the 2-year prevalence of high risk plaque morphology features between treatment groups using chi-squared (or Fisher's exact) tests as appropriate; these analyses will be performed overall and by subgroups defined by the presence of NCP at study entry.

*Sample table from Testosterone study, JAMA 2017*

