## Appendix I Sample Size Considerations

[Copied Verbatim from the REPRIEVE A5333S Protocol, Version 5.0, Section 9.2.]

The target sample size for the Mechanistic Substudy of REPRIEVE (A5333s) is 800 participants that will be approximately equally distributed between the study arms.

This sample size was determined to have high power to detect clinically relevant differences between the two study groups both with respect to plaque progression (among those with plaque at study entry) and rates of incident plaque (among those plaque-free at entry). Specifically, the total sample size of 800 subjects will provide 90% power to detect a 6% difference between the study groups in the percent change in NCP volume over 2 years among those with plaque at entry and 90% power to detect 13 percentage point difference in the probability of plaque development over 2 years. These effect sizes translate to a combined estimated 14 percentage point difference in the probability of NCP progression over two years and are based on the following assumptions:

50% of study participants will have evidence of NCP at study entry [Lo 2010]

A SD of 20% for the percent change over 2 years among participants with evidence of plaque at entry

An annual rate of incident plaque development of 12% among participants without plaque at entry

15% of participants entering the substudy will not be evaluable for study entry or 2 year NCP volume.

Together, the effects of statins acting in these two groups (those with and without evidence of NCP at study entry) will provide for a 7% lower prevalence of NCP after 2-years of statin treatment. Expectations for NCP prevalence and progression both as a whole and according to whether NCP was present at study entry are illustrated in the table below. These estimates are based on a simulation that further assumed the following:

Average volume NCP 250mm^3 (SD=200) among participants with NCP at entry.

Average volume NCP 40mm^3 (SD=20) at 2 years among participants without NCP at entry without statin treatment.

Average volume NCP 20mm^3 (SD=20) at 2 years among participants without NCP at entry with statin treatment.

NCP distributions were also assumed to follow a gamma distribution with size and shape parameters determine to provide the desire mean and standard deviations.

Table 9.2-1: Cells constituting the primary targeted group comparisons are shown in bold.

		At study entry			At two 2 years						

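### SAP 7.2 does not name the strata of the whole-population test of NCP progression; adding entry NCP status to sex and CD4 would recover roughly a quarter of the information

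*SAP*

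**What the plan says.** SAP 3.2.2 labels NCP progression a primary outcome and defines it by entry status. For one group it is new plaque: "Among participants without evidence of NCP at entry on the qualitative read, evidence of NCP at 2 years". For participants with NCP at entry it is any volume increase. Where the qualitative and quantitative reads disagree, the quantitative read decides.

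SAP 7.2 then takes the population as a whole: "progression over two years (see Section 3.2.2) will be compared by treatment group using a stratified chi-squared test". It does not say what the strata are. Sex and CD4 are named as strata for the volume regression in the same section, as adjustment factors in the primary estimand table (SAP 2.1), and as the randomization factors in SAP 4.1. Protocol 9.6.1 sets them as the general rule for all testing. Entry NCP is not named as a stratum of the pooled test in either document.

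Protocol Appendix II, 9.5.1, notes that "Since CCTA will not be available at the time of randomization, balance by treatment arm cannot be guaranteed within these subgroups". The same sentence goes on to expect relative balance, given the sample size and the stratification.

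**The concern.** Pooling participants whose chance of the outcome differs greatly for a known pre-treatment reason puts avoidable variance into the comparison. Entry NCP comes from the entry scan, so it costs nothing to use. The other primary outcome, change in NCP volume, is already adjusted for baseline NCP volume, while SAP 7.1 asks for baseline adjustment of continuous outcomes only. The binary primary outcome therefore gets none. At stake is the precision of a primary comparison, and its power if the true effect is smaller than planned. It also leaves the strata of a primary test unwritten.

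**Working it through.** **Inputs.** Two-sided 5% test: "All primary treatment group comparisons will be performed ITT using a 5% type error" (SAP 7.1) and "Statistical comparisons will be performed using two-sided significance tests with a 5% Type I error" (Protocol 9.6.1). From SAP Appendix I: 800 participants, 1:1, 15% not evaluable, 50% with NCP at entry. That leaves 800 × 0.85 = 680 evaluable, or 340 per arm and 170 per arm in each entry group. Table 9.2-1 gives incident NCP of 21% (control) and 8% (statin) without plaque at entry. With plaque at entry, percent change has mean 12% and 5%, SD 20%, with 5th and 95th percentiles of −14 and 49 (control) and −21 and 43 (statin).

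**The missing probability.** The table does not print the chance of any increase among those with plaque, so it must be modelled. A shifted gamma with the table's means and SD, fitted to its percentiles, gives 69.2% (control) and 53.3% (statin). A normal distribution gives 72.6% and 59.9%.

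**The plan's own figure.** The plan states a "combined estimated 14 percentage point difference in the probability of NCP progression over two years". Under the gamma fit:
- control: 0.5 × 0.692 + 0.5 × 0.21 = 0.451
- statin: 0.5 × 0.533 + 0.5 × 0.08 = 0.306
- difference: 14.4 points, which reproduces the 14.

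The component claim of "90% power to detect 13 percentage point difference in the probability of plaque development over 2 years" also reproduces: 12% a year is 1 − 0.88² = 22.6% over two years, and 22.6% vs 9.6% with 170 per arm gives 90.7% power. The claim that "the total sample size of 800 subjects will provide 90% power to detect a 6% difference between the study groups" does not: 6 points with SD 20 and 170 per arm gives 79.0%. The table's 7 points (12% vs 5%) gives 89.7%. Both effects are carried below.

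**Loss of information (gamma fit).** Compare the summed binomial variances of the two arms, ignoring and respecting entry NCP:
- ignoring it: 0.451 × 0.549 + 0.306 × 0.694 = 0.460; SE = √(0.460/340) = 3.68 points
- respecting it: 0.5 × (0.692 × 0.308 + 0.533 × 0.467) + 0.5 × (0.21 × 0.79 + 0.08 × 0.92) = 0.351; SE = √(0.351/340) = 3.21 points
- information lost: 1 − 0.351/0.460 = 24%; extra scans needed: 0.460/0.351 − 1 = 31%.

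**Power.** Φ[(d − 1.96 × SE₀)/SE], with SE₀ the null standard error from the arm-averaged probabilities:
- without the stratum: (14.45 − 1.96 × 3.72)/3.68 = 1.95, giving 97.4%
- with it: (14.45 − 1.96 × 3.26)/3.21 = 2.51, giving 99.4%.

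| Model for those with plaque | Progression with plaque, control vs statin | Information lost | Extra scans | Power without → with stratum |
|---|---|---|---|---|
| Shifted gamma (matches the table's percentiles) | 69.2% vs 53.3% | 24% | 31% | 97.4% → 99.4% |
| Lognormal | 70.9% vs 56.5% | 26% | 35% | 95.7% → 99.0% |
| Gamma on the ratio | 71.3% vs 57.5% | 27% | 36% | 94.8% → 98.7% |
| Normal, 12% vs 5% | 72.6% vs 59.9% | 28% | 39% | 92.9% → 98.1% |
| Normal, 12% vs 6% | 72.6% vs 61.8% | 29% | 41% | 88.6% → 96.4% |

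A separate simulation with a gamma of shape 4, comparing sex × CD4 strata with the same strata plus entry NCP, gave mean test statistics of 3.80 and 4.32. Then (4.32/3.80)² = 1.29, so 29% more scans or 1 − 1/1.29 = 23% lost.

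**Smaller effect.** Shrinking both gamma-model differences to 75% (69.2% vs 57.2%, and 21% vs 11.25%) gives d = 10.8 points, SEs of 3.73 and 3.26, and power of 82.5% without and 91.1% with the stratum.

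**Validity.** In 20,000 simulated null trials, type I error was 5.1% without the stratum and 4.9% with it.

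**Do sex and CD4 stand in for entry NCP?** Little, on an assumed case: with 20% women, and NCP in 30% of women and 55% of men, the between-sex variance is 0.8 × 0.05² + 0.2 × 0.20² = 0.010, or 4% of 0.25.

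**The case against.** The other side has several good points.

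- The SAP does not say that entry NCP is left out; it leaves the strata unnamed. That stands. The firm finding is an unspecified stratification, with sex and CD4 inferred from the general rule. Appendix II, 9.5.1, also plans analyses by entry-NCP subgroup by default, but as separate analyses, not as strata of a pooled test.
- SAP 7.2 already compares the arms within each entry group, and the sample size rests on those comparisons. True, but they do not sharpen the pooled test of an outcome labelled primary.
- Power at the planned effect is already high. True; the gain matters mainly if the effect is smaller. SAP Appendix I concedes that no data directly inform the clinical relevance of the assumed differences.
- The model assumes a clean no-NCP group. Discordant reads, which SAP 3.2.2 allows for, could change the gain.

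A reader might infer more than the documents support. One inference is that the plan admits imbalance in entry NCP. Appendix II says only that balance is not guaranteed, and expects it. Another is that chance imbalance biases the estimate on top of the lost precision. A one-SD imbalance is √(2 × 0.25/340) = 3.8 points, and it moves the difference by 3.8 × (0.612 − 0.145) = 1.8 points. But √(3.68² − 3.21²) is also 1.8: it is the same variance, already in the wider standard error. A third is to take the 29–41% as information lost. Those are extra scans; the loss is 23–29%.

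**Conclusion.** The point holds as a matter of specification and precision. The strata of a primary test are not written down. On the reading that the rest of the plan supports, they omit a strongly prognostic baseline factor that also determines which event counts. The cost is roughly a quarter of the information.

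The size rests on 340 evaluable participants per arm, 50% with NCP at entry, the table's 21% and 8%, and an assumed shape for percent change. The shape that matches the table's percentiles and the 14 points gives 24%. If entry NCP prevalence were 30–70% (an assumed range), the loss would be 19–29% across the gamma and normal (12% vs 5%) models. The planned test is valid, and adequately powered at the planned effect; the documents do not support calling it biased.

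**What to change.** In SAP 7.2, state that NCP progression will be compared with a Cochran-Mantel-Haenszel test stratified by entry NCP (present or absent on the entry qualitative read), sex and CD4, and reported as a stratum-weighted risk difference with 95% CI. Naming the read matters because the quantitative read settles discordant progression. The interval is needed because SAP 7.1 specifies one only for continuous outcomes. Treat total plaque progression in the same way, with entry plaque (present or absent on the entry qualitative read) as the stratum.

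The cost is one or two sentences and no new data. Eight strata in about 680 participants average 85 each, which is workable for this test. If the analysis has already been run under the current SAP, report the stratified result as a labelled sensitivity analysis.

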### 2.2 Secondary Objectives

- To determine the effects of pitavastatin on the progression of high risk plaque features including low attenuation plaque and positive remodeling.
- To determine the effects of pitavastatin on detailed markers of immune function including, immune activation (%CD14+CD16+ monocytes, sCD163, sCD14, MCP-1 and T-cell markers), inflammation (Lp-PLA2, hsCRP, hs troponin, oxLDL IL-6), coagulation (D-Dimer) and traditional CVD risk indices

including detailed parameters of glucose homeostasis (insulin, glucose and related indices of insulin resistance such as HOMA-IR).

- To determine the relative contributions of baseline and pitavastatin induced changes in HIV-specific immune activation and traditional risk factors, including LDL, on the presence and progression of coronary plaque and high-risk morphological features in HIV.

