### 3.3 Exploratory Plaque Outcomes

The following are additional CT-related outcomes that will be described for the cohort at entry and year 2, as appropriate. *Note: Not all of these analyses will be included in the primary manuscript; but will be included in the packet of primary analyses for completeness.*

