3.3.3 Presence of vulnerable plaque features

- Five binary (Yes, No) outcomes based on the qualitative read
- Presence of any following vulnerable features (main outcome) and the prevalence of each feature descriptively (four outcomes)
  - Positive remodeling
  - Low attenuation plaque
  - Positive remodeling and low attenuation plaque
  - Napkin ring sign

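### The year-2 test of any vulnerable plaque feature ignores whether the feature was present at entry and is unstratified, unlike the plaque tests beside it

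*SAP*

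**What the plan says.** SAP section 7.2 (under the table of primary and secondary plaque outcomes) sets the test for high-risk features as "comparing differences in the 2-year prevalence of high risk plaque morphology features between treatment groups using chi-squared", with Fisher's exact test as the alternative. It is run overall and again in subgroups by presence of noncalcified plaque (NCP) at entry. Protocol Appendix II, section 9.5.2, has the same unstratified test, so the two documents agree.

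The outcome is defined in SAP 3.3.3: "Presence of any following vulnerable features (main outcome) and the prevalence of each feature descriptively (four outcomes"). It sits in section 3.3, whose items are "additional CT-related outcomes that will be described for the cohort at entry and year 2, as appropriate". It nevertheless serves a secondary objective in SAP 2.2: "To determine the effects of pitavastatin on the progression of high risk plaque features including low attenuation plaque and positive remodeling".

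The general rule on baseline in SAP 7.1 reaches only one type of outcome: "For continuous outcomes, inference will be based on differences in means adjusted for baseline". A binary feature outcome is not covered.

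**The concern.** A vulnerable feature seen at entry may well still be there two years later. If so, entry status is a strong predictor of year-2 status, it is read from scans the substudy already takes, and the test does not use it. Two things follow. Random differences between arms in entry prevalence stay in the estimate, and the test has less power than the same data could give. Also, a comparison of year-2 prevalence combines features that appeared, persisted or resolved, whereas the objective is worded in terms of progression.

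The stake is limited to one secondary objective of the substudy. Neither type I error nor the primary NCP analyses are affected.

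**Working it through.** **1. The tests in SAP 7.2 side by side**

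| Outcome | Test | Use of entry scan | Strata |
|---|---|---|---|
| Change in NCP volume | Linear regression | Baseline volume as covariate | Sex, CD4 |
| Incident NCP | Chi-squared | Restricted to no NCP at entry | Stratified, strata not named |
| NCP and total plaque progression | Chi-squared: "will be compared by treatment group using a stratified chi-squared test" | Outcome defined relative to entry (3.2.2) | Stratified, strata not named |
| High-risk features | Chi-squared or Fisher | None for the feature; repeated by entry NCP | None |

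**2. Validity.** Let Y0 and Y2 be feature presence at entry and year 2. Randomization makes E(Y0) equal in the two arms, so the expected difference in Y2 equals the expected difference in Y2 − Y0. The planned contrast is therefore unbiased for the difference in net change, given the plan's assumption that absent scans are missing completely at random.

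**3. Inputs from the plan.** SAP Appendix I targets 800 participants, equally split, and states that "15% of participants entering the substudy will not be evaluable for study entry or 2 year NCP volume". That leaves 800 × 0.85 / 2 = 340 per arm. No power is stated for the feature test. The nearest binary figure is 90% power for a 13-point difference in incident NCP among the 50% without NCP at entry, or 170 per arm. Two-year control incidence is 1 − 0.88² = 22.6%. For 22.6% against 9.6% with pooled variance under the null,

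(0.13 × √170 − 1.96 × √(2 × 0.1606 × 0.8394)) / √(0.2256 × 0.7744 + 0.0956 × 0.9044) = (1.695 − 1.018) / 0.511 = 1.325,

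which is 90.7% power. The stated figure reproduces, so the same sample size is used below.

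**4. What omitting entry status costs, by formula.** With entry prevalence p, persistence s and new appearance i, year-2 prevalence is q = ps + (1 − p)i, and the entry-to-year-2 correlation is

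r = √(p(1 − p)) × (s − i) / √(q(1 − q)).

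Adjusting for entry removes a share r² of the outcome variance. For p = 25%, s = 80%, i = 5%: q = 23.75%, r = 0.433 × 0.75 / 0.4256 = 0.76, r² = 0.58.

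The imbalance behind this is visible directly. The standard deviation of the between-arm difference in entry prevalence is √(2 × 0.25 × 0.75 / 340) = 3.3 points. Of that, 0.75 × 3.3 = 2.5 points pass into a year-2 difference whose own standard error is √(2 × 0.2375 × 0.7625 / 340) = 3.3 points.

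**5. Simulation.** 20,000 trials per scenario, 340 per arm, same odds ratio on persistence and new appearance, set so that the crude test has about 80% power. Prevalence, persistence and new appearance are assumed.

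| Entry / persistence / new | r | Crude power | Stratified on entry feature | Gain (points) |
|---|---|---|---|---|
| 5% / 30% / 10% | 0.14 | 81.0% | 81.4% | 0.4 |
| 5% / 60% / 10% | 0.33 | 80.4% | 84.6% | 4.2 |
| 10% / 60% / 10% | 0.42 | 80.3% | 86.7% | 6.4 |
| 25% / 30% / 10% | 0.24 | 80.6% | 82.4% | 1.8 |
| 25% / 60% / 10% | 0.52 | 80.4% | 89.6% | 9.2 |
| 25% / 80% / 5% | 0.76 | 79.8% | 98.1% | 18.3 |
| 40% / 80% / 5% | 0.77 | 80.3% | 98.0% | 17.7 |

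Type I error is 4.5% to 5.4% for both tests. With 5% fewer participants in the stratified test, the gain runs from −1.6 to +17.8 points.

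**6. Sensitivity to the assumed effect.**
- Reaching 80% crude power needs odds ratios of about 0.32 to 0.49, and the largest gains need the strongest of these.
- At an odds ratio of 0.5 the gain is about 1 to 33 points. At 0.7 it is about 1 to 14 points, with both tests at or below about 36% power.
- A separate set of scenarios used entry prevalence 10–30%, persistence 60–90%, new appearance 5–10%, and treatment lowering persistence by 20% and new appearance by 40% in relative terms. Crude power was 29–57%. Stratifying on sex and CD4 alone changed it by at most about 1 point. Adding the entry feature brought it to 54–93%.
- If treatment halves only the odds of new features (25% / 80% / 5%), power is 8.7% crude and 14.9% stratified.

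**The case against.** The strongest reply is that nothing here is an error. The test is valid, the outcome is exploratory, SAP and protocol agree, and every power figure rests on assumed inputs. All of that stands, and it caps the importance of the point.

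Other parts of the reply stand in part:

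- Low-attenuation plaque volume (SAP 3.3.5) is continuous, so the baseline rule in 7.1 gives one of the two named features an adjusted comparison. It does nothing for the binary outcome that 3.3.3 calls the main one.
- Among participants without NCP at entry, a feature at year 2 is effectively new if these are features of noncalcified plaque, as Protocol Appendix II section 1.1 describes them. That subgroup test is then close to an incidence comparison. In the assumed 50% with NCP at entry the distinction is still lost.
- The neighbouring chi-squared tests say they are stratified without naming strata; sex and CD4 are an inference from the regression sentence and the randomization. Protocol section 9.6.1 requires sex and CD4 stratification of all testing, but it is written for the main trial. Sex and CD4 bring consistency with the randomization and almost no power.
- The adjusted test still has year-2 presence as its outcome. Progression is answered only by describing new and resolved features alongside it.
- Sparse strata could trouble a logistic model at low prevalence. A Cochran-Mantel-Haenszel test over eight sex-by-CD4-by-entry strata kept its type I error in simulation.
- SAP 1.0 is dated March 2023 and 1.1 was prepared for release with the published data. If results by arm are already known, replacing the planned test would be post hoc.

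**Conclusion.** The point holds as a matter of efficiency and fit to the objective. The gain comes almost entirely from entry presence of the feature and depends on persistence: negligible at a correlation of 0.14, about 9 points at 0.52, and about 18 points near 0.77 when the crude test has 80% power. It turns slightly negative if features hardly persist and some entry scans are missing. The text reading is certain; the magnitude is conditional on inputs the documents do not supply. This is a low-priority, optional change.

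**What to change.** In SAP 7.2, for the outcome of any vulnerable feature, make the treatment comparison a Cochran-Mantel-Haenszel test stratified by entry presence of any vulnerable feature, sex and screening CD4, in participants with paired scans. Report the stratum-adjusted difference in prevalence with a 95% confidence interval. Describe new appearance and resolution by arm. Keep the individual features descriptive, so that no tests are added, and keep crude year-2 prevalence from all available year-2 scans as a supportive summary. State whether the repeats by entry NCP use the same stratified test. Record the departure from Protocol Appendix II section 9.5.2 in the version history. If treatment-group results are already known, keep the planned test and label the adjusted one as supportive.

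The cost is a sentence, a version-history entry and a little programming, with no new data. The price is that participants without an entry scan leave the adjusted test.
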